9.1. PK Sampling Schedule

Plasma samples will be taken at baseline (pre-infusion) and at the following time points after start of infusion: 5 min \pm 1 min, 15 min \pm 1 min, 25 min \pm 1 min, 30 min - 1 min (the infusion will not be stopped before the 30-min plasma sample has been collected), 45 min \pm 5 min, 1 h \pm 5 min, 1 h 30 \pm 5 min, 4 h \pm 5 min, 8 h \pm 5 min, and 24 h \pm 2 hour (based on protocol version 4.0). In the case of conversion from atrial fibrillation during infusion, an additional sample will be taken immediately after conversion.

9.2. Derived and Imputed Data for PK Endpoint

For all sampling times, the actual sampling times will be calculated as the difference between the sample collection actual clock time and the actual clock time of start of the infusion of AP30663. The actual post-dose sampling times expressed in hours and rounded off to three decimal digits will be used to calculate the PK parameters, except for pre-dose samples occurring prior to infusion, which will always be reported as zero (0.000), regardless of the time difference.

For NCA approach, the following PK parameters including, but not limited to, will be determined for each patient based on plasma concentrations:

- $AUC_{0-0.5}$: Area under the concentration time curve from pre-dose concentration up to 30 min. $AUC_{0-0.5}$ includes the plasma drug concentration up to the end of infusion
- AUC_{0-t} : Area under the concentration time curve up to the last measurable concentration
- $AUC_{0-\infty}$: Area under the concentration time curve from pre-dose through concentration to infinity (extrapolated), calculated as $AUC_{0-t} + C_t/K_{el}$, where C_t is the last observed non-zero concentration
- C_{max} : The observed peak drug concentration
- T_{max} : The time at which C_{max} occurs
- $t_{1/2}$: the terminal half-life value will be calculated using the equation $\ln 2 / K_{el}$, with K_{el} being the elimination rate constant
- K_{el} : Elimination rate constant. This parameter will be the negative of the estimated slope of the linear regression of the ln-transformed concentration versus time profile in the terminal elimination phase. At least 3 concentration points will be used in estimating K_{el} . The time point where ln-linear K_{el} calculation begins (K_{el} Lower), and the actual sampling time of the last quantifiable concentration used to estimate the K_{el} (K_{el} Upper) will be reported with the correlation coefficient from the linear regression to calculate K_{el} .

From the developed population PK model (Pop-PK), PK parameters like volume of distribution and clearance will be estimated. Additional PK parameters including, but not limited to, area under the curve at steady-state (AUC_{ss}) will be derived from the individual Bayes estimates from the pop-PK model. A separate analysis plan will be created to detail this approach.

This document is confidential.

9.2.1. Handling of Dropouts, Particularities, Missing Data or Data Below the Lower Limit of Quantification

Missing concentration data for all patients who are administered scheduled study treatment will be considered as non-informative missing and will not be imputed. No concentration estimates will be provided for missing sample values.

For NCA approach, plasma concentrations below the limit of quantification (BLQ) will be set to zero in the computation of mean concentration values; however, BLQ concentrations between 2 non-BLQ concentrations will be set to missing. For the computation of PK variables, the BLQ concentrations prior to the first measurable concentration will be set to zero and other BLQ concentrations will be set to missing.

Samples taken far outside the sampling windows may be excluded from by-time point summary statistics; this will be determined prior to database lock.

9.3. Planned Statistical Models for PK Parameters and Concentrations

The plasma concentration at each time point will be summarized as n, number and percentage BLQ, arithmetic and geometric mean, SD and arithmetic coefficient of variation (CV (%)) (calculated as $100 \times SD / \text{mean}$), median, minimum and maximum

Descriptive statistics (n, arithmetic mean, SD, arithmetic CV (%), geometric mean, geometric CV(%), minimum, median and maximum) by treatment group will be calculated for all derived PK endpoints.

The following conventions will be used for the presentation of the descriptive statistics of PK parameters and of plasma concentrations:

PK Reporting Precision

Statistics	Degree of Precision
Minimum, Maximum	In the same precision as PK results, i.e. with 3 decimal places
Mean (arithmetic and geometric), Median	one more decimal place than the PK results, i.e. with 4 decimal places
Standard deviation	Two more decimal places than the PK results, i.e. with 5 decimal places
CV and Geometric CV	1 decimal place

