In rats, daily 1-hour infusions for 2 weeks caused a reversible dose-related local infusion site inflammation at all dose levels, with associated lung inflammation and thromboembolism. No other toxicity of human relevance was observed up to the highest dose tested, 90 mg/kg/day, which was considered the NOAEL for toxicity not related to the local infusion site reactions.

The maximally tolerated exposure in minipigs and rats appeared to be comparable, meaning that the 2 species may be regarded as similarly sensitive. A total (free and bound) exposure level (C_{max}) of approximately 11,000 ng/mL was seen at the highest dose in both minipigs (25 mg/kg) and rats (90 mg/kg), and this dose level should not be exceeded in humans unless carefully evaluated.

Two phase 1 Single Ascending Dose trials investigating the safety and tolerability of AP30663 in healthy male subjects at doses up to 8 mg/kg have been completed. The trials showed that the infusion with AP30663 caused mild and transient infusion site reactions as well as prolongation of the QTcF-interval but was otherwise well tolerated at all administered dose levels. The effect on QTcF was dose and plasma concentration related with a peak estimated mean QTcF prolongation of 45.2 ms for the dose of 6 mg/kg. The QTcF effect was transient and a return to baseline level was observed 8 hours after the start of administration for the 6 mg/kg dose, consistent with low plasma concentrations at this timepoint.

No effects were found on heart rate, blood pressure or other ECG markers. No CNS effects were found, including based on a sensitive assessment of tremors (tremorography).

The aim of this study is to show proof of concept, (i.e. the ability of AP30663 to terminate ongoing AF episodes) and 1 or more dose levels will be compared with placebo.

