8.3.4.2 Treatment Discontinuation (Stop of Infusion)

The planned duration of drug infusion is described in [Section 8.4.1](#).

Criteria for stop of drug infusion prior to cardioversion or prior to the infusion duration of 30 min are as follows:

- Developing hemodynamic instability (drop in BP, drop in heart rate, unless caused by conversion) including but not limited to
 - systolic BP decrease to <90 mm Hg or significant decrease from baseline (e.g. >40 mm Hg), or mean BP decrease <70 mm Hg (calculated as [systolic BP + 2 × diastolic BP] / 3).
 - systolic BP increase to >190 mm Hg or
 - heart rate <40 bpm or
 - intolerable side effects.
- Developing changes in ECG variables (compared with pre-infusion ECG):
 - QRS +50% and/or development of BBB.
 - QTcF +60 ms.
 - QTcF >500 ms.
- Developing tremors (involuntary, rhythmic muscle contraction leading to shaking movements in one or more parts of the body)
- Per investigator decision, when it is not in the patient's best interest to continue infusion. Specific attention should be paid to any other AEs related to the central nervous system and/or any local infusion site reactions.

Pregnancy

Patients will be instructed that known or suspected pregnancy occurring during the study, in female patients or female partners of male patients, should be confirmed and reported to the investigator. The investigator should also be notified of any pregnancy occurring during the study but confirmed only after completion of the study. In the event that a patient is subsequently found to be pregnant after inclusion in the study, any pregnancy will be followed to term, and the status of mother and child will be reported to Acesion Pharma after delivery.

Full details will be recorded in the eCRF and a pregnancy reporting form will be completed (see [Section 10.1.3.1.1](#)).

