5.5. Safety Set

All randomised patients who were administered double-blind study treatment. Patients will be analysed according to the treatment received. The Safety Set will be used for all analyses of safety endpoints.

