5.6. Pharmacokinetic (PK) Set

The PK Set will include all patients in the Safety Set who have at least one evaluable post-infusion drug concentration value.

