10.1. Extent of Exposure

Extent of exposure will be summarized by treatment group for duration of infusion .

Duration of infusion will be derived as:

Duration of infusion (in min)= (Stop Time of Study Drug Infusion- Start Time of Study Drug Infusion) – duration of infusion interruption

Extent of exposure (expected total volume to infuse and infused volume) will be summarized by treatment group.

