Table 14.3.1.6	Treatment-Emergent Adverse Events by System Organ Class, Preferred Term, and Maximum Severity	Safety Set	
Table 14.3.4.1.1.1	Summary statistics of Laboratory Data: Haematology	Safety Set	
Table 14.3.4.1.1.2	Change from Baseline in Laboratory Data: Haematology	Safety Set	
Table 14.3.4.1.1.3	Laboratory Data: Haematology Relationship to Reference Range – Shift from Baseline	Safety Set	

This document is confidential.

Table Number	Name	Analysis Set	Delivered for Interim analysis/DMC
Table 14.3.4.1.1.4	Laboratory Data: Haematology Clinical Significance	Safety Set	
Table 14.3.4.1.2.1	Summary statistics of Laboratory Data: Clinical Chemistry	Safety Set	
Table 14.3.4.1.2.2	Change from Baseline in Laboratory Data: Clinical Chemistry	Safety Set	
Table 14.3.4.1.2.3	Laboratory Data: Clinical Chemistry Relationship to Reference Range – Shift from Baseline	Safety Set	
Table 14.3.4.1.2.4	Laboratory Data: Clinical Chemistry Clinical Significance	Safety Set	
Table 14.3.4.2.1	Summary of Vital Signs	Safety Set	
Table 14.3.4.2.2	Change from Baseline in Vital Signs	Safety Set	✓
Table 14.3.4.3.1	Summary of 12-Lead ECG Parameters	Safety Set	
Table 14.3.4.3.2	Change from Baseline in 12-Lead ECG Parameters	Safety Set	✓
Table 14.3.4.3.3	12-Lead ECG Clinical Significance	Safety Set	✓
Table 14.3.4.3.4	12-Lead ECG QTc Intervals: Categorical Analysis	Safety Set	✓
Table 14.3.4.4	Brief Physical Examination - Shift from Baseline	Safety Set	

This document is confidential.

17. Index of Figures

Figure Number	Figure Title	Delivered for Interim analysis/DMC
Figure 14.2.2.1.3	Kaplan-Meier curve for Time to Conversion from AF – Full analysis set	
Figure 14.2.3.3	Mean (\pm SD) Plasma Concentration - Linear and Semi-Log Scales - PK Set	✓ For interim analysis this graph will be provided by the PK group
Figure 14.2.3.4	Overlay of Individual and Mean AP30663 Plasma Concentrations by Treatment - Linear and Semi-Log Scales - PK Set	✓ For interim analysis this graph will be provided by the PK group
Figure 14.2.3.5	Scatter plot of Plasma Concentration Immediately After Conversion versus Time to Conversion – PK set	
Figure 14.2.3.6	Mean (\pm SD) Cmax vs. AP30663 Dose Level - PK Set	
Figure 14.2.3.7	Mean (\pm SD) AUC0-t vs. AP30663 Dose Level - PK Set	
Figure 14.2.3.8	Mean (\pm SD) AUC0-0.5 vs. AP30663 Dose Level - PK Set	
Figure 14.2.3.9	Scatter Plot of Cmax vs. Time to Conversion - PK Set	
Figure 14.2.3.10	Scatter Plot of AUC0-t vs. time to conversion- PK Set	

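### NCA exposure is reported by nominal dose with truncated and full infusions pooled; AUC normalised to the dose received is missing and cheap to add.

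*SAP*

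**What the plan says.** **Summary and plots.** SAP 9.3 states that descriptive statistics "by treatment group will be calculated for all derived PK endpoints" (Table 14.2.3.2). SAP Section 17 lists plots such as "Cmax vs. AP30663 Dose Level - PK Set" (Figure 14.2.3.6), with AUC0-t and AUC0-0.5 in Figures 14.2.3.7 and 14.2.3.8.

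**Who is included.** SAP 5.6: "The PK Set will include all patients in the Safety Set who have at least one evaluable post-infusion drug concentration value". There is no exclusion, flag or separate handling for an incomplete infusion. The parent Safety Set follows the rule "Patients will be analysed according to the treatment received" (SAP 5.5), which settles which treatment a patient counts under, not how much of it was infused.

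**Early stops are foreseen.** Protocol 8.3.4.2 introduces its list with "Criteria for stop of drug infusion prior to cardioversion or prior to the infusion duration of 30 min are as follows". One item is a QTcF rise of 60 ms from the pre-infusion ECG. Protocol 8.4.9 records early termination and its reason.

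**What is reported about them.** SAP 10.1 summarises infusion duration, and "Extent of exposure (expected total volume to infuse and infused volume) will be summarized by treatment group". SAP 10.2 counts full and interrupted infusions with reasons. SAP 5.7 makes a stop before 30 min a major deviation, tabulated and listed on the Randomised Set. Listing 16.2.5.1 covers drug administration. None of these feeds into the PK outputs.

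**The concern.** A patient stopped halfway through a 5 mg/kg infusion stays in the 5 mg/kg column and plot point with the AUC of about 2.5 mg/kg. If stops were rare and unrelated to dose or exposure, this would be noise. They are probably not unrelated. Protocol Section 6 describes the QTcF effect as dose- and concentration-related, with a "peak estimated mean QTcF prolongation of 45.2 ms for the dose of 6 mg/kg", and a QTcF rise is itself a stop criterion. Stops would then fall mainly at the higher doses and in the patients with the highest exposure, so the dose-exposure relation would be flattened at its upper end.

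The trial is meant to identify a dose for later research, and the influence of dose on PK is an exploratory objective. The Section 9.3 table and the dose-level figures are where a reader would look for that relation.

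**Working it through.** The documents give no expected stop rate, stop time or exposure, so there is no planned figure to reproduce.

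**1. Dose received is derivable from planned data.** Protocol 8.4.2 gives mL = kg × mg/kg ÷ 2, at 2 mg/mL for every dose. At 80 kg and 5 mg/kg the expected volume is 80 × 5 ÷ 2 = 200 mL. Stopped at 15 min of 30 at a constant rate, 100 mL is infused. Percent of intended dose = 100 ÷ 200 = 50%, and 50% × 5 = 2.5 mg/kg received. Cross-check: 100 × 2 ÷ 80 = 2.5.

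Infused volume alone is not a dose. In the 3 mg/kg arm, 75 mL is 3.0 mg/kg at 50 kg, but 75 × 2 ÷ 110 = 1.4 mg/kg at 110 kg. Infused volume over expected volume is the fraction given, because weight cancels.

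**2. Effect of a stop on mean AUC.** Under linear PK, AUC0-inf is proportional to the fraction delivered. With share f stopped at fraction q, the mean falls by f × (1 − q). One of 12 stopped at 10 min: (1/12) × (1 − 10/30) = 5.6%. The geometric mean falls by 1 − (1/3)^(1/12) = 8.7%.

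**3. Do stops cluster at high doses?** Assume a peak effect linear in dose and a between-patient SD of 10-25 ms (not in the documents). The chance of reaching +60 ms at the peak is 1 − Φ((60 − 45.2d/6)/SD):

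| SD | 3 mg/kg | 5 mg/kg | 6 mg/kg |
|---|---|---|---|
| 10 ms | 0.0% | 1.3% | 6.9% |
| 15 ms | 0.6% | 6.8% | 16.2% |
| 20 ms | 3.1% | 13.2% | 23.0% |
| 25 ms | 6.7% | 18.6% | 27.7% |

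The gradient supports the direction. These are chances at the peak, so they overstate stops before 30 min if the peak comes at or after the end of infusion.

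**4. Size, with QTcF following concentration.** Assumptions: lognormal exposure with CV 25-35%; one compartment with effective half-life 5-60 min; QTcF rise proportional to concentration, with mean 45.2 × d/6 ms at the end of infusion; 8 ms measurement error; infusion stopped if the rise exceeds 60 ms at a check. Understatement of mean AUC by simulation:

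| QTcF checks | 5 mg/kg | 6 mg/kg |
|---|---|---|
| One, at 10 or at 20 min | 0-4% | 0-8% |
| Both, at 10 and 20 min | 0-5% | 1-11% |

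The upper ends need a 5 min half-life and CV 35%. With both checks and a half-life of 10 min or more, the 6 mg/kg figure is 1-6%. At 3 mg/kg the effect is negligible. A true 6:3 AUC ratio of 2.0 with an 8% loss at 6 mg/kg would be reported as 2.0 × 0.92 = 1.84. More frequent checks would produce more stops and larger losses.

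**5. Cmax moves less than AUC.** A stopped patient's Cmax is the fraction r = (1 − e^(−k·30q)) ÷ (1 − e^(−k·30)) of the full value. With f = 20% and q = 1/2, mean AUC falls by 0.2 × 0.5 = 10%. Mean Cmax falls by 0.6%, 2.2%, 5.2% and 9.1% for half-lives of 3, 5, 10 and 60 min.

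**6. Would complete infusions alone cure it?** No. In the step 4 model at 6 mg/kg, with a 5 min half-life and one check at 20 min, the complete-only mean AUC is 0.95 (CV 25%) and 0.90 (CV 35%) of the full-dose value. Pooling gives 0.95 and 0.92. Dropping stopped patients removes the highest exposures.

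**The case against.** The strongest reply is that little depends on these outputs. They are descriptive. SAP 4.4 takes the PK endpoints from the population PK model, whose handling of infusion records belongs to a separate plan. Table 14.2.3.2 and Figures 14.2.3.6 to 14.2.3.8 are not marked for interim delivery, and the algorithm in SAP 11 uses conversion rate only. The 6 mg/kg arm opens only if 5 mg/kg closes for low response. All of this stands and limits the weight of the point. It does not correct the NCA table or the figures.

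A reader might infer more than the documents support:

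- *That exposure at the top doses is understated as a matter of fact.* No stop rate is given, and with no stops there is no bias.
- *That the dose received cannot be recovered.* SAP 10.1 collects expected as well as infused volume, so only the derived quantity is missing.
- *That an early stop matters only for the Per-Protocol Set.* SAP 5.7 and 10.2 also tabulate it.
- *That the bias could reach 18% at 6 mg/kg.* A figure of that size comes from applying the full 45.2 ms at 10 min, although the protocol gives it as a peak effect.
- *That Cmax suffers as AUC does.* Protocol Section 6 reports an early plateau in animals; if that holds in patients, Cmax changes little.
- *That the exposure-QTcF relation is distorted.* Each patient's own Cmax and AUC are still correctly observed, and the sample code in SAP Appendix I plots QTcF against measured concentration.

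**Conclusion.** The point holds in a limited, conditional form. The SAP pools truncated and full infusions under the nominal dose and relates no NCA parameter to the amount given. If stops concentrate at higher doses, mean AUC there is biased low, and Cmax to a lesser degree. A reasonable size is 0-8% at 6 mg/kg and 0-4% at 5 mg/kg, rising to about 11% and 5% with two QTcF checks, fast kinetics and CV 35%. In small arms a single early stop is worth about 6%. These sizes rest on the assumed variability, half-life and timing of checks, and they cover only stops from the QTcF rise.

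Two ambiguities bear on how often truncation happens. Protocol 8.1.2 and 9.3 and SAP 9.1 say the infusion is not stopped before the 30-min sample, whereas Protocol 8.3.4.2 provides for stops before 30 min. The ECG timing after conversion in Protocol 8.1.2 and 9.3 also leaves unclear whether conversion ends the infusion; if it does, truncation could be far more common than modelled here. This is a low-cost improvement to the PK reporting and does not threaten the trial's main conclusions.

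**What to change.** 1. **SAP 10.1:** derive per patient the percent of intended dose (infused volume ÷ expected volume) and mg/kg received (that percent × nominal dose). Summarise both by arm in Table 14.1.5.1.
2. **SAP 9.3, Table 14.2.3.2:** add AUC0-t and AUC0-inf normalised to mg/kg received, for all PK Set patients. Under linear PK this removes the bias exactly for AUC0-inf, and closely for AUC0-t where little is extrapolated. AUC0-0.5 is left out because its fixed 30-min window no longer matches the end of infusion in a stopped patient.
3. **Figures 14.2.3.6 to 14.2.3.8:** mark stopped infusions, or plot against mg/kg received.
4. Do not make a complete-infusion-only summary the main one, for the reason in step 6 of the working.
5. Reconcile the statements on stopping before the 30-min sample (Protocol 8.1.2 and 9.3, SAP 9.1) with Protocol 8.3.4.2, and state whether conversion ends the infusion.

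Items 1 to 4 cost two derived variables from data already recorded, a few table rows and a plotting symbol. Item 5 is a wording reconciliation for the sponsor.

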9.4. PK Interim Analyses

After all patients in Part 1 have completed Day 2, corresponding to 24 hours after the stop of the infusion, an unblinded interim analysis (IA) will be performed using NCA and pop-PK model. The list of Topline Results for the interim analyses are described below for each method of derivation:

This document is confidential.

NCA:

- Mean (\pm SD) AP30663 Plasma Concentrations - Linear and semi-Log Scales – PK Set
- Overlay of Individual and Mean AP30663 Plasma Concentrations by Treatment - Linear and semi-Log Scales - PK Set

These figures will be also provided during Part 2 where IAs will occur when 18, 36 and 54 patients have been randomised to open-doses including placebo, and have completed Day 2 assessments or terminated the study.

Pop-PK model:

Interim results including average PK parameters determination will be provided using descriptive statistics and graphical evaluation. A summary report including conclusion/recommendation for the dose of Part 2 will be generated.

9.5. Deviation from Analyses Planned in Protocol

No deviation from PK analyses described in the Protocol is planned.

This document is confidential.

10. Safety

The population used for safety analyses will be the Safety Set (SS). Safety will be assessed on the basis of adverse event (AE) or adverse drug reactions (ADR) reports, clinical laboratory data, ECG parameters, physical examinations, and vital signs.

10.1. Extent of Exposure

Extent of exposure will be summarized by treatment group for duration of infusion .

Duration of infusion will be derived as:

Duration of infusion (in min)= (Stop Time of Study Drug Infusion- Start Time of Study Drug Infusion) – duration of infusion interruption

Extent of exposure (expected total volume to infuse and infused volume) will be summarized by treatment group.

10.2. Treatment Compliance

Number (%) of patients completing the full infusion treatment, number (%) of patients with infusion interruption and reasons for stopping will also be summarized.

10.3. Adverse Events / Adverse Drug Reactions

AEs will be coded using the Medical Dictionary for Regulatory Activities (MedDRA) version 21.1 or an updated version. Summaries will be presented by system organ class (SOC) and preferred term. Treatment-emergent AEs (TEAEs) are defined as any AE occurring or worsening on or after the first dose of study medication. Partial AE dates will be imputed.

The frequency and incidence of TEAEs will be presented by SOC and preferred term for each treatment group (number and percentage of patients experiencing at least one TEAE per preferred term as well as the number of observed events per preferred term; percentages will be based on the number of patients in the safety set).

The summaries presenting frequency of AEs by SOC and PT will be ordered by overall descending frequency of SOC and then, within a SOC, by overall descending frequency of PT.

Separate tables will be presented by severity and by relationship, and for SAEs, related TEAEs, and TEAEs leading to study discontinuation.

Relationships of 'very likely', 'probable' and 'possible' are to be considered as related to study drug for the summary tables. Relationships of 'unlikely' and 'unrelated' are to be considered not related to study drug.

In case of missing relationships, AEs will be considered as related.

All AEs will be presented in full in a comprehensive listing including patient number, treatment group, severity, seriousness, action taken, outcome, relationship to treatment, onset/stop, and duration. TEAEs will be flagged in the listings.

This document is confidential.

Details of SAEs and AEs leading to withdrawal will be listed separately.

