- n ECG print-outs: within 15 min before infusion start, at 10 min after infusion start, and, in case of conversion from AF, within 1 min after conversion BUT before infusion stop. Diagnosis of AF (defined as absence of discrete P waves and an irregular ventricular rate) to be confirmed based on a 12-lead ECG. On Day 2 the ECG should be completed 24 h +/- 2 hours after infusion start.
- o Continued assessment to start 30 min before infusion. Holter to stop after the PK sampling at 8 h. Telemetry to continue for minimum 8 h after infusion start.
- p Should be done in all patients; mandatory if not done within 6 months (inclusive) before randomisation.
- q Heart rhythm, LV size, LV area, LVEF, atrial area and size as well as other clinically significant finding results to be provided or requested if available.
- r In case of AF persistence at 90 min after start of infusion, a direct-current electrical cardioversion is to be done within 180 min post-infusion start (200 J biphasic synchronised).
- s Recording of any AEs/SAEs will start after the ICF has been signed. From infusion start, special attention should be paid to AEs related to the central nervous system including tremors.

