8.4.8.2 Rescue Medication

All patients who will not convert from AF during infusion of the study drug or within 90 min after the infusion start should undergo DC electrical cardioversion within 180 min from the time the infusion started. DC electrical cardioversion should be performed using biphasic synchronised cardioverter with energy of 200 J.

All medications necessary for direct-current electrical cardioversion (e.g. sedatives) should be administered per local standards, observing limitations from [Section 8.4.8.1](#) (Prohibited Medication and Procedures), and should be recorded as concomitant medications.

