10.1.3.1.1 Serious Adverse Events

Serious Adverse Event Definition

An SAE is any untoward medical occurrence or effect that, at any dose,

- Results in death.
- Is life-threatening. (An AE is life-threatening if the patient was at immediate risk of death from the event as it occurred, i.e. it does not include a reaction that might have caused death if it had occurred in a more serious form.)
- Requires or prolongs inpatient hospitalisation. (Complications occurring during hospitalisation are AEs and are SAEs if they cause prolongation of the current hospitalisation. Hospitalisation for elective treatment of a pre-existing non-worsening condition is not, however, considered an AE. The details of such hospitalisations must be recorded on the medical history or physical examination page of the eCRF.)
- Results in persistent or significant disability/incapacity. (An AE is incapacitating or disabling if it results in a substantial and/or permanent disruption of the patient's ability to carry out normal life functions.)
- Results in a congenital anomaly/birth defect.

In addition, medical and scientific judgement is required to decide if prompt notification is required in situations other than those defined for SAEs above. This may include any event that the investigator regards as serious that did not strictly meet the criteria above but may have jeopardised the patient or required intervention to prevent one of the outcomes listed above, or that would suggest any significant hazard, contraindication, side effect, or precaution that may be associated with the use of the investigational product.

Note that if DC cardioversion is performed as indicated in the schedule of assessments (Section 8.1.2), it should not be reported as AE/SAE.

Reporting of Serious Adverse Events

Any SAE must be reported by the investigator if it occurs during the clinical study from signing of the ICF or within 30 days of receiving the study drug, whether or not the SAE is considered to be related to the investigational product. An SAE report consists of the SAE form. A copy of these forms must be faxed **within 24 h** for the attention of the product safety scientist at

Syneos Health Safety and Pharmacovigilance Department
[contact] or
Email: [contact]

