4.5. Safety Endpoints

- Adverse events (AEs), electrocardiogram (ECG) variables including significant arrhythmia, physical examination, vital signs, and laboratory evaluations.
- Changes in QTcF interval data over time.

This document is confidential.

5. Analysis Sets

For purposes of analysis, the following populations are defined for both Parts 1 and 2.

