8.2. Secondary Efficacy Endpoint(s) and Analyses

8.2.1. Time to conversion from AF from start of infusion

The time to conversion from AF from start of infusion will be analysed using Kaplan-Meier methods. The number of patients that reached cardiac conversion within 90 mins of start of study drug infusion will be summarized using the median time to cardiac conversion along with the interquartile range (IQR).

A Kaplan Meir plot stratified by treatment group will be presented. A logrank test will be used to compare treatment groups.

Time to conversion (in min) will be calculated using the formulae:

This document is confidential.

Time to conversion (in min) = (Time of conversion or censoring - time of start of infusion).

In case of AF persistence at 90 min after start of infusion, a direct-current (DC) electrical cardioversion is to be done within 180 min post-infusion start. Patients who have electrical cardioversion will be censored. The time of censoring will be 90 min.

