8.2.2. Proportion of patients with relapse of AF within 5 min (IRAF)

The proportion of patients with relapse of AF within 5 min (IRAF) following pharmacological or DC cardioversion will be presented by treatment and analysed using a logistic regression model. The model will include treatment, and duration of current AF episode.

In addition the same analysis will be done for the proportion of patients with relapse of AF within 5 min (IRAF) following pharmacological cardioversion only.

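### Arrhythmia TEAE counts run across the rescue DC shock, so they can dilute a drug excess at doses that convert well; a supplementary 0-90 min table by dose is a cheap, optional improvement

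*SAP*

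**What the plan says.** - **Endpoint.** SAP 4.5 names "electrocardiogram (ECG) variables including significant arrhythmia" among the safety endpoints. No title in the SAP's indexes of tables, figures and listings (sections 16 to 18) is dedicated to arrhythmia.
- **Counting rule.** SAP 10.3: "Treatment-emergent AEs (TEAEs) are defined as any AE occurring or worsening on or after the first dose of study medication". Protocol 10.1.3.1 follows AEs for 30 days. The planned AE tables break down by SOC and preferred term, severity, relationship, seriousness and discontinuation. None breaks down by time from infusion or by shock.
- **Rescue shock.** For AF persisting at 90 min, the footnotes to Protocol 8.1.2 state that "a direct-current electrical cardioversion is to be done within 180 min post-infusion start". Protocol 8.4.8.2 says that patients not converted by 90 min "should undergo DC electrical cardioversion within 180 min from the time the infusion started".
- **AE exemption.** Of a cardioversion performed as scheduled, Protocol 10.1.3.1.1 says "it should not be reported as AE/SAE". That exempts the procedure, not an arrhythmia that follows it.
- **Efficacy.** Here the SAP does separate the shock. For time to conversion (8.2.1), "Patients who have electrical cardioversion will be censored", at 90 min. For IRAF (8.2.2), the analysis is repeated "following pharmacological cardioversion only".
- **DMC outputs.** The AE tables ticked for the DMC are 14.3.1.1 (overall), 14.3.1.3 (related) and 14.3.1.4 (serious). The SOC/preferred-term table 14.3.1.2, the compliance table 14.1.5.2 and the AE listing 16.2.7.1 are not ticked.

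**The concern.** The shock is given after randomisation, and who receives it depends on whether the dose worked. If some shocks are followed by an arrhythmia reported as an AE, the arm with more shocks collects more of these events. That arm is placebo, or a dose that converts poorly. A drug-caused excess before 90 min is then compared with a placebo count raised by the shock.

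The direction matters because doses are opened and closed on conversion rate, with DMC safety review as the check. A dose that looks best on conversion also has the fewest shocks, so the pooled count leans in its favour. The introduction to the protocol reports a peak estimated mean QTcF prolongation of 45.2 ms at 6 mg/kg, so arrhythmia is a natural safety question for this drug.

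**Working it through.** **Inputs from the documents** (Protocol 17.3, illustrative final data):
- Example 1: Dose 5 28/36 converted, placebo 6/42.
- Example 2: Dose 6 24/36, Dose 3 4/18, placebo 8/42.

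As a check that these examples are read correctly, the Beta(1+28, 1+8) posterior gives Pr(P > 0.65) = 0.941; the protocol states 0.94.

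**Step 1: share eligible for the shock** = 1 − conversion. This treats primary-endpoint non-response as AF at 90 min, which is an approximation.

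| Comparison | Drug | Placebo | Gap (points) |
|---|---|---|---|
| Ex 1, Dose 5 | 8/36 = 22.2% | 36/42 = 85.7% | 63.5 |
| Ex 2, Dose 6 | 12/36 = 33.3% | 34/42 = 81.0% | 47.6 |
| Ex 2, Dose 3 | 14/18 = 77.8% | 34/42 = 81.0% | 3.2 |

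**Step 2: pooled difference.** Two quantities are assumed, because the documents give neither:
- s, the risk of an arrhythmia AE per shocked patient, the same in both arms;
- d, the drug-caused excess, all of it before 90 min.

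Background is set to zero.
- Placebo pooled rate = share_placebo × s.
- Drug pooled rate = 1 − (1 − d)(1 − share_drug × s).

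Example for Ex 1 Dose 5, d = 5 points, s = 2%: placebo 0.857 × 0.02 = 1.7%; drug 1 − 0.95 × (1 − 0.222 × 0.02) = 5.4%; difference 3.7 points, a loss of 1.3.

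Pooled drug-minus-placebo difference in points, d = 5:

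| s | Ex 1 Dose 5 | Ex 2 Dose 6 | Ex 2 Dose 3 |
|---|---|---|---|
| 0% | +5.0 | +5.0 | +5.0 |
| 2% | +3.7 | +4.0 | +4.9 |
| 5% | +1.8 | +2.5 | +4.6 |
| 10% | −1.5 | +0.1 | +4.3 |

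**Step 3: rate at which the excess vanishes.** s = d / (share_placebo − (1 − d) × share_drug).
- Ex 1 Dose 5, d = 5: 0.05 / (0.857 − 0.95 × 0.222) = 7.7%; with d = 10, 15.2%.
- Ex 2 Dose 6, d = 5: 10.1%.
- Ex 2 Dose 3, d = 5: 71%, so in practice never.

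**Step 4: chance that the drug arm shows a rate no higher than placebo** (exact binomial, Ex 1 Dose 5, 36 vs 42):

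| s | d = 5 | d = 10 |
|---|---|---|
| 0% | 0.16 | 0.02 |
| 2% | 0.19 | 0.04 |
| 5% | 0.34 | 0.12 |
| 10% | 0.59 | 0.32 |

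For Ex 2 Dose 3 (18 vs 42, d = 5) the chances are 0.40, 0.31, 0.28 and 0.33, so pooling does not raise them.

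**Step 5: what a 0-90 min table would show.** Under the same assumptions the difference is d whatever s is, since no planned shock has yet been given. If a quarter of drug-caused events came after 90 min, a 10-point excess would show as 7.5. The early table should therefore supplement the full window, not replace it.

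**The case against.** The case against acting is substantial, and most of it stands.

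- **The full-window count answers a valid question**: total harm under drug plus rescue. It would also catch a drug that makes the shock itself riskier, which a 0-90 min table would miss. The protocol reports QTcF returning to baseline only at 8 h for 6 mg/kg.
- **The DMC sees more than AE tables.** It reviews unblinded ECG and Holter data, and Holter records are available to it at the interim analyses (Protocol 10.1.1.1, 10.2). The ECG clinical-significance table (14.3.4.3.3) and the 12-lead ECG listing (16.2.8.3) are ticked for it. ECGs are extracted at the PK times through 90 min, so QTcF there is unaffected by the planned shock.
- **The related-TEAE table filters on blinded causality.** An arrhythmia just after a shock can be rated unrelated and drop out. The filter is imperfect, because a rating of possible counts as related.
- **Infusion-stop reasons are a pre-shock count.** SAP 10.2 says "number (%) of patients with infusion interruption and reasons for stopping will also be summarized", and the stopping criteria include heart rate below 40 bpm and new bundle branch block. This covers only events that stopped the infusion, and the table is not ticked for the DMC.
- **Tabulation by preferred term** keeps many drug-type and shock-type events on different rows. The dilution modelled here applies to an SOC or overall row.
- **An early window can mislead the other way.** Protocol 8.3.4.2 recognises that conversion itself can lower heart rate. With an assumed 5% rate of such events at conversion, Example 1 would show a spurious excess of 63.5% × 5% = 3.2 points against Dose 5. The fix must handle this.

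A reader might infer that the plan hides arrhythmia harm from the DMC, or that no pre-shock comparison exists. The documents do not support either reading. The cover above is real, and the DMC Charter (which sets the data to be reviewed), the cardiac SAP and the eCRF were not supplied. What remains is that, in the supplied SAP, no pre-specified by-arm arrhythmia table stops before the planned shock.

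**Conclusion.** The point holds as an optional improvement, not as an error. The TEAE tables pool arrhythmias across a rescue shock whose frequency follows the non-conversion rate, and the lean favours doses that convert well. The effect is small at a 2% post-shock rate and is a clear dilution at 5%. A 5-point excess is cancelled only at about 8-10%. For a dose that converts like placebo there is almost no effect.

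These sizes rest on the protocol's illustrative data, an assumed post-shock rate equal in both arms, and drug-caused events all before 90 min. The documents support no particular post-shock rate, so it would go too far to say that masking is likely or that the TEAE definition is wrong.

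**What to change.** Keep the full-window TEAE tables. In SAP 10.3 or 10.6 and section 16, add one supplementary Safety Set table by dose, ticked for the DMC:

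1. Arrhythmia events with onset 0-90 min from infusion start, as the between-arm comparison before any planned shock. List any off-protocol shock given earlier.
2. Events from 90 min to 8 h, shown descriptively by shocked or not shocked, because the drug effect may persist.
3. Bradycardia and pauses at the moment of conversion on a separate row, for both pharmacological and DC conversion, so that the early window does not count them only against the effective dose.

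Take onset times from Holter, telemetry or the eCRF. If the cardiac SAP or DMC Charter already provides this, add a cross-reference instead.

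**Cost:** one extra table, largely from rhythm data already recorded. A data-transfer specification or an onset-time field may also be needed, since the AE fields listed in Protocol 10.1.3.1 give only the date of first occurrence.
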